12.6 Psoriasis Scalp Severity Index

The PSSI considers both the extent of the area of involvement and the severity based on the scoring scales outlined in [Table 12-2](#). The assessment considers erythema, induration, and desquamation on the scalp. For each of these 3 elements, the scores of the area and severity are multiplied. Then, the score from each element is totaled to obtain the PSSI score. As with the

PASI, the PSSI score ranges from 0 to 72 with a higher score indicating increased scalp disease severity.

The PSSI will be assessed at the visits specified in [Table 5-1](#).

Table 12-2: Parameters assessed for the PSSI

Assessment of extent of scalp psoriasis	
Score	Definition
1	<10%
2	10-29%
3	30-49%
4	50-69%
5	70-89%
6	90-100%
Assessment of clinical symptoms (erythema, induration, and desquamation)	
Score	Definition
0	Absent
1	Slight
2	Moderate
3	Severe
4	Severest possible

PSSI=Psoriasis Scalp Severity Index

12.7 PGADA for the arthritis VAS

The PGADA for the arthritis VAS will be used to provide an overall evaluation of arthritis disease symptoms. Subjects will respond to the question, “Considering all the ways your arthritis affects you, please mark a vertical line on the scale below to show how you are feeling today,” using a VAS where 0 is “very good, no symptoms” and 100 is “very poor, severe symptoms.”

Each subject will complete the PGADA at the visits specified in [Table 5-1](#).

12.8 36-Item Short Form Health Survey

The SF-36 (Version 2, standard recall) is a 36-item generic health-related QOL instrument that uses a recall period of 4 weeks. Items are grouped into 8 domains as follows: Physical Functioning (10 items), Role Physical (4 items), Bodily Pain (2 items), General Health (5 items), Vitality (4 items), Social Functioning (2 items), Role Emotional (3 items), Mental Health (5 items), and 1 item for perceived stability or change in health (Health Transition) during the last year. The concepts represented by these domains contribute to physical, mental, and social aspects of health-related QOL. In addition to domain scores, the PCS and MCS scores are calculated from the 8 domains (excluding the Health Transition item). Component scores

appreciate the impact of each domain on physical and mental health status (Maruish, 2011). Each of the 8 domain scores and the component summary scores range from 0 to 100, with a higher score indicating a better health status. The domains and the 2 component summary scores are standardized with a mean of 50 and a standard deviation of 10 in the general USA population. The minimally important differences, in terms of T-score points, for SF-36 domains and component summaries are as follows: PCS, 2; MCS, 3; Physical Functioning, 3; Role-Physical, 3; Bodily Pain, 3; General Health, 2; Vitality, 2; Social Functioning, 3; Role-Emotional, 4; and Mental Health, 3 (Maruish, 2011).

The SF-36 will be completed by the subject the visits specified in [Table 5–1](#).

12.9 Hospital Anxiety and Depression Scale

The HADS was chosen for its well-established psychometric properties and its use in clinical research on biological therapy in subjects with chronic plaque psoriasis (Dauden et al, 2009; Langley et al, 2010). The HADS scores for anxiety and for depression range from 0 to 21 with higher scores indicating worse state. A score below 8 is considered to be normal (Snaith and Zigmond, 1994).

13 STUDY MANAGEMENT AND ADMINISTRATION

13.1 Adherence to protocol

The Investigator should not deviate from the protocol. However, the Investigator should take any measure necessary in deviation from or not defined by the protocol in order to protect clinical study subjects from any immediate hazard to their health and safety. In this case, this action should be taken immediately, without prior notification of the regulatory authority, IRB/IEC, or Sponsor.

After implementation of such measure, the Investigator must notify the Clinical Project Manager of the Sponsor within 24 hours and follow any local regulatory requirements.

13.2 Monitoring

UCB (or designee) will monitor the study to meet the Sponsor's monitoring Standard Operating Procedures (SOPs), ICH-GCP guideline, and applicable regulatory requirements, and to ensure that study initiation, conduct, and closure are adequate. Monitoring of the study may be delegated by UCB to a CRO or a contract monitor.

The Investigator and his/her staff are expected to cooperate with UCB (or designee) and to be available during the monitoring visits to answer questions sufficiently and to provide any missing information. The Investigator(s)/institution(s) will permit direct access to source data/documents for study-related monitoring, audits, IRB/IEC review, and regulatory inspection(s).

The Investigator will allow UCB (or designee) to periodically review all eCRFs and corresponding source documents (eg, hospital and laboratory records for each study participant). Monitoring visits will provide UCB (or designee) with the opportunity to evaluate the progress of the study, verify the accuracy and completeness of eCRFs, ensure that all protocol requirements, applicable authorities regulations, and Investigator's obligations are being fulfilled, and resolve any inconsistencies in the study records.

13.2.1 Definition of source data

All source documents must be accurate, clear, unambiguous, permanent, and capable of being audited. Source documentation should be made using some permanent form of recording (ink, typing, printing, optical disc). They should not be obscured by correction fluid or have temporary attachments (such as removable self-stick notes). Photocopies of eCRFs are not considered acceptable source documents. Source documents are original records in which raw data are first recorded. These may include hospital/clinic/general practitioner records, charts, diaries, x-rays, laboratory results, printouts, pharmacy records, care records, ECG or other printouts, completed scales, or QOL questionnaires, for example. Source documents should be kept in a secure, limited access area.

The Sponsor or designee will review to ensure that computerized source documents produced by the site are compliant with Food and Drug Administration (FDA) Part 11 requirements and document appropriately. Source documents that are computer generated and stored electronically that are not FDA Part 11 compliant, must be printed for review by the monitor (eg, ECG reports). Once printed, these copies should be signed and dated by the Investigator and become a permanent part of the subject's source documents. The Investigator will facilitate the process for enabling the monitor to compare the content of the printout and the data stored in the computer to ensure all data are consistent.

Electronic data records, such as Holter monitor records or electroencephalogram records, must be saved and stored as instructed by the Sponsor or designee.

Patient Reported Outcome (PRO) measures (eg, DLQI, SF-36, and PGADA) will be completed by each subject utilizing electronic data capture.

13.2.2 Source data verification

Source data verification ensures accuracy and credibility of the data obtained. During monitoring visits, reported data are reviewed with regard to being accurate, complete, and verifiable from source documents (eg, subject files, recordings from automated instruments, tracings [ECG], x-ray films, laboratory notes). All data reported on the eCRF should be supported by source documents, unless otherwise specified in Section 13.2.1.

13.3 Data handling

13.3.1 eCRF completion

This study will use electronic data capture (EDC); the Investigator is responsible for prompt reporting of accurate, complete, and legible data in the eCRF and in all required reports.

This study will use an electronic device to capture patient reported outcomes (see [Section 13.2.1](#)).

Serious AE reporting will be done using the SAE Form (see [Section 9.2.2](#)) while also entering the event in the appropriate eCRF section. The safety database and the clinical database will be reconciled during the study and discrepancies will be corrected as needed.

The Investigator should maintain a list of personnel authorized to enter data into the eCRF. Access to the EDC will be given after training has been received. A training certificate will be provided and filed.

Detailed instructions on the use of the EDC will be provided in the eCRF Completion Guidelines.

Corrections made after the Investigator's review and approval (by means of a password/electronic signature) will be re-approved by the Investigator. Any change or correction to the eCRF after saving must be accompanied by a reason for the change.

13.3.2 Database entry and reconciliation

Case Report Forms/external electronic data will be entered/loaded into a validated electronic database using a clinical data management system. Computerized data cleaning checks will be used in addition to manual review to check for discrepancies and to ensure consistency of the data. This study is performed using EDC: the data are entered into the eCRFs once and are subsequently verified.

An electronic audit trail system will be maintained to track all data changes in the database once the data have been saved initially into the system or electronically loaded. Regular backups of the electronic data will be performed.

13.3.3 Subject Enrollment log/Subject Identification Code list

The subject's enrollment will be recorded in the Subject Enrollment Log.

The Investigator will keep a Subject Identification Code list. This list remains with the Investigator and is used for unambiguous identification of each subject.

The subject's consent and enrollment in the study must be recorded in the subject's medical record. These data should identify the study and document the dates of the subject's participation.

13.4 Termination of the study

UCB reserves the right to temporarily suspend or prematurely discontinue this study either at a single site, multiple sites, or at all sites at any time for reasons including, but not limited to, safety or ethical issues, inaccurate or incomplete data recording, noncompliance, or unsatisfactory enrollment with respect to quality or quantity.

If the study is prematurely terminated or suspended, UCB (or its representative) will inform the Investigators/institutions and the regulatory authority(ies) of the termination or suspension and the reason(s) for the termination or suspension, in accordance with applicable regulatory requirement(s). The IRB/IEC should also be informed and provided with reason(s) for the termination or suspension by the Sponsor or by the Investigator/institution, as specified by the applicable regulatory requirement(s). In addition, arrangements will be made for the return of all unused IMP and other material in accordance with UCB procedures for the study.

13.5 Archiving and data retention

The Investigator will maintain adequate records for the study, including eCRFs, medical records, laboratory results, Informed Consent documents, drug dispensing and disposition records, safety reports, information regarding participants who discontinued, and other pertinent data.

All essential documents are to be retained by the Investigator until at least 2 years after the last approval of a marketing application in an ICH region and until there are no pending or contemplated marketing applications in an ICH region, or at least 2 years have elapsed since the

formal discontinuation of clinical development of the IMP. These documents should be retained for a longer period, however, if required by the applicable regulatory requirement(s) or by an agreement with UCB (Committee for Proprietary Medicinal Products [CPMP]/ICH/135/95, 2002 [Section 4.9.5]). The Investigator will contact UCB for authorization prior to the destruction of any study records or in the event of accidental loss or destruction of any study records. The Investigator will also notify UCB should he/she relocate or move the study-related files to a location other than that specified in the Sponsor's study master file.

13.6 Audit and inspection

The Investigator will permit study-related audits mandated by UCB, after reasonable notice, and inspections by domestic or foreign regulatory authorities.

The main purposes of an audit or inspection are to confirm that the rights and well-being of the subjects enrolled have been protected, that enrolled subjects (ie, signing consent and undergoing study procedures) are appropriate for the study, and that all data relevant for the evaluation of the IMP have been processed and reported in compliance with the planned arrangements, the protocol, investigational site, and IRB/IEC SOPs, ICH GCP, and applicable regulatory requirements.

The Investigator will provide direct access to all study documents, source records, and source data. If an inspection by a regulatory authority is announced, the Investigator will immediately inform UCB (or designee).

13.7 Good Clinical Practices

Noncompliance with the protocol, ICH-GCP, or local regulatory requirements by the Investigator, institution, institution staff, or designees of the Sponsor will lead to prompt action by UCB to secure compliance. Continued noncompliance may result in the termination of the site's involvement in the study.

14 STATISTICS

A description of statistical methods is presented below and will be described in more detail in the Statistical Analysis Plan (SAP).

14.1 Definition of analysis sets

The Enrolled Set (ES) will consist of all subjects who have given informed consent for PS0011.

The Safety Set (SS) will consist of all subjects who receive at least 1 dose of the study medication in PS0011.

The Full Analysis Set (FAS) will consist of all enrolled subjects who receive at least 1 dose of the study medication in PS0011 and have a valid efficacy measurement for PASI at Baseline of PS0011.

The Pharmacokinetics Per-Protocol Set (PK-PPS) will consist of all enrolled subjects who receive at least 1 dose of the study medication in PS0011 and provide at least 1 quantifiable plasma concentration postdose in PS0011.

14.2 General statistical considerations

No inferential statistical analyses are planned for this extension study. Instead, all variables will be presented using summary statistics. For categorical variables, counts and percentages will be displayed. For continuous variables, summary statistics will consist of the number of available observations, arithmetic mean, standard deviation, median, minimum, and maximum unless stated otherwise.

Because subjects entering PS0011 may or may not be continuing on the same dose as that received in PS0010, there are various combinations of treatment that could be received when considering both PS0010 and PS0011 together. For describing the summaries to be produced, treatment groups will be categorized as either the PS0011 treatment groups or PS0010/PS0011 treatment groups. These categorizations are outlined below.

PS0011 treatment groups

This refers to the study treatment assigned to the subject at the beginning of PS0011 and does not account for the treatment received in PS0010. The PS0011 treatment groups are as follows:

- Placebo
- Bimekizumab 64mg Q4W
- Bimekizumab 160mg Q4W
- Bimekizumab 320mg Q4W
- All Bimekizumab (optional – to be used only if specified)

PS0010/PS0011 treatment groups

This refers to the combination of the randomized treatment in PS0010 and the treatment assigned at the beginning of PS0011. Some groups have been combined where it is considered appropriate to do so. The PS0010/PS0011 treatment groups with descriptions are as follows:

- Placebo to Placebo – Subjects randomized to placebo in PS0010 who achieve PASI90 response at Week 12 of PS0010 and continue to receive placebo in PS0011.
- Placebo to Bimekizumab 160mg Q4W – Subjects randomized to placebo in PS0010 who do not achieve PASI90 response at Week 12 of PS0010 and are treated with bimekizumab 160mg Q4W in PS0011.
- Bimekizumab 64mg to Bimekizumab 64mg – Subjects randomized to bimekizumab 64mg Q4W in PS0010 who achieve PASI90 response at Week 12 of PS0010 and continue to receive bimekizumab 64mg Q4W in PS0011.
- Bimekizumab 64mg to Bimekizumab 160mg – Subjects randomized to bimekizumab 64mg Q4W in PS0010 who do not achieve PASI90 response at Week 12 of PS0010 and are treated with bimekizumab 160mg Q4W in PS0011.
- Bimekizumab 160mg Q4W to Bimekizumab 160mg Q4W – Subjects randomized to bimekizumab 160mg Q4W or bimekizumab 320mg loading dose + 160mg Q4W in PS0010 who achieve PASI90 response at Week 12 of PS0010 and continue to receive bimekizumab

160mg Q4W in PS0011. Note that the PS0010 160mg Q4W groups with and without the loading dose are combined here.

- Bimekizumab 160mg Q4W to Bimekizumab 320mg Q4W – Subjects randomized to bimekizumab 160mg Q4W or bimekizumab 320mg loading dose + 160mg Q4W in PS0010 who do not achieve PASI90 response at Week 12 of PS0010 and are treated with bimekizumab 320mg Q4W in PS0011. Note that the PS0010 160mg Q4W groups with and without the loading dose are combined here.
- Bimekizumab 320mg Q4W to Bimekizumab 320mg Q4W – Subjects randomized to bimekizumab 320mg Q4W in PS0010 and continue on 320mg Q4W in PS0011. No distinction will be made between subjects that were or were not PASI90 responders at Week 12 of PS0010.
- Bimekizumab 480mg Q4W to Bimekizumab 320mg Q4W – Subjects randomized to bimekizumab 480mg Q4W in PS0010 and continue on 320mg Q4W in PS0011. No distinction will be made between subjects that were or were not PASI90 responders at Week 12 of PS0010.

The treatment groups to be used in the presentations of safety and efficacy will depend on the objective of the summaries and will be specified accordingly.

14.3 Planned safety analyses

Safety variables will be analyzed for all subjects in the SS.

Adverse events will be coded according to the Medical Dictionary for Regulatory Activities (MedDRA[®]). Treatment-emergent AEs will be defined as events that have a start date on or following the first administration of study treatment in PS0011 through the final administration of study treatment +140 days (covering the 20-week SFU Period). Treatment-emergent AEs will be categorized by PS0011 treatment group. Tables will include columns for placebo, bimekizumab 64mg Q4W, bimekizumab 160mg Q4W, bimekizumab 320mg, and All bimekizumab (ie, any dose of bimekizumab).

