7.2 Treatments to be administered

During the Treatment Period, all subjects will receive bimekizumab or placebo Q4W administered sc (refer to [Figure 5–1](#) for further details).

Subjects who received placebo or bimekizumab 64mg, 160mg, or 320mg loading dose + 160mg Q4W in PS0010 must achieve PASI90 response at Week 12 in PS0010 to enter the PS0011 extension study on the same treatment dose. Subjects who do not achieve PASI90 response at Week 12 in PS0010 while on these treatments will be assigned to receive bimekizumab 160mg or 320mg Q4W at Baseline in PS0011 as follows:

- Subjects receiving placebo and bimekizumab 64mg Q4W in PS0010 will be assigned to bimekizumab 160mg Q4W in PS0011.
- Subjects receiving bimekizumab 160mg Q4W and 320mg loading dose + 160mg Q4W in PS0010 will be assigned to bimekizumab 320mg Q4W in PS0011.

Subjects who receive bimekizumab 320mg or 480mg Q4W in PS0010 will be assigned to receive bimekizumab 320mg Q4W on entering PS0011, regardless of their PASI90 response at Week 12 in PS0010.

The study medication is to be administered in the clinic by study site staff as 2 sc injections for all study treatments in PS0011. Suitable areas for sc injections are the lateral abdominal wall and upper outer thigh. Injection sites should be rotated, and injections should not be given into areas where the skin is tender, bruised, red, or hard.

The minimum time between doses should be no less than 24 days and no more than 32 days for Q4W dosing.

An IMP Handling Manual will be provided to each site containing instructions regarding drug preparation and dosing.

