14.3.2 Other safety analyses

Additional tables will summarize TEAEs by intensity and relationship to study medication, TEAEs leading to withdrawal from the study, treatment-emergent SAEs, and deaths. Other AE summaries to be included will be specified in the SAP. All AE tables will be presented by PS0011 treatment group (including the All bimekizumab group).

Extent of exposure to study medication in PS0011 will be summarized using descriptive statistics by PS0011 treatment group.

Change from Baseline in laboratory values, ECGs, and vital signs will be presented using descriptive statistics by PS0010/PS0011 treatment group. As these variables are summarized over time and the initial values can be impacted by the randomized treatment in PS0010, the presentation by PS0010/PS0011 treatment group is intended to provide perspective on the change in these values starting with the initial PS0010 randomization through the 48-week Treatment Period of PS0011. The table presentations will display descriptive statistics for the PS0010 Baseline followed by descriptive statistics for the observed, change from PS0010 Baseline, and change from PS0011 results by scheduled visit for PS0011.

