3.6 Treatment assignment and treatment groups

At Baseline, eligible subjects will be assigned as described in [Section 2.3.2](#). Summaries using the FAS will be based on treatments according to the assignment and not actual treatment received.

It is expected that subjects will receive treatment as assigned. Hence, safety analyses should be based on assigned treatment for the SS. However, if it is determined after unblinding that subjects assigned to placebo received bimekizumab at any time, then these subjects will be reallocated to the appropriate bimekizumab group and will be summarized accordingly from the time point at which the misallocation occurred. If a subject receives different doses of bimekizumab at different time points, then the subject will be allocated to the highest dose received. If the highest dose was received earlier than the other(s), then all safety data will be summarized under that dose. If the highest dose was received later than the other(s), then safety data will be summarized under that dose starting from the time point at which it was first received. Since the period of exposure at risk includes an additional 140 days following the last dose of study medication, no consideration is given to the time at which exposure to misallocated doses can be considered complete.

Subjects assigned to a bimekizumab group will only be reallocated to the placebo treatment group if they never received bimekizumab.

Because subjects entering PS0011 may or may not be continuing on the same dose as that received in PS0010, there are various combinations of treatment that could be received when considering both PS0010 and PS0011 together. For describing the summaries to be produced, treatment groups will be categorized as either the PS0011 treatment groups or PS0010/PS0011 treatment groups. The categorizations are outlined below.

PS0011 treatment groups

This refers to the study treatment assigned to the subject at the beginning of PS0011 and does not account for the treatment received in PS0010. The PS0011 treatment groups are as follows:

- Placebo
- Bimekizumab 64mg Q4W
- Bimekizumab 160mg Q4W
- Bimekizumab 320mg Q4W
- All Bimekizumab (optional – to be used only if specified)

PS0010/PS0011 treatment groups

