8.1.6 Analysis of the primary safety variable

All TEAEs will be summarized descriptively by PS0011 treatment group, primary SOC, HLT, and PT. This summary will include the number and percentage of subjects experiencing the event, the number of events, EAIR with associated 95% confidence interval based upon the Chi-Square distribution (Ulm, 1990), and the EAER.

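### The primary TEAE tables by PS0011 dose confound dose with prior exposure: all first-time bimekizumab users sit in the 160mg column

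*Protocol*

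**What the plan says.** The grouping is the same in both documents. Protocol 14.3 says "Treatment-emergent AEs will be categorized by PS0011 treatment group". SAP 8.1.6, for the primary variable, says "All TEAEs will be summarized descriptively by PS0011 treatment group, primary SOC, HLT, and PT", with EAIR, its 95% confidence interval, and EAER. SAP 3.6 says that this grouping "does not account for the treatment received in PS0010". The time at risk starts at the first PS0011 dose (Protocol 14.3.1, SAP 8.1.3).

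The assignment rules decide who is in each column:

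- **160mg.** For PASI90 non-responders, Protocol 7.2 says "Subjects receiving placebo and bimekizumab 64mg Q4W in PS0010 will be assigned to bimekizumab 160mg Q4W in PS0011". Former 160mg responders, with or without the loading dose, stay here too.
- **64mg.** Protocol 14.2 describes this group as "Subjects randomized to bimekizumab 64mg Q4W in PS0010 who achieve PASI90 response at Week 12 of PS0010 and continue to receive bimekizumab 64mg Q4W".
- **320mg.** Protocol 7.2 sends former 160mg non-responders here: "Subjects receiving bimekizumab 160mg Q4W and 320mg loading dose + 160mg Q4W in PS0010 will be assigned to bimekizumab 320mg Q4W in PS0011". It adds, whatever the response, "Subjects who receive bimekizumab 320mg or 480mg Q4W in PS0010 will be assigned to receive bimekizumab 320mg Q4W on entering PS0011".
- **Placebo.** Only placebo PASI90 responders remain on placebo.

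SAP 8.2.1 also plans a TEAE table and a serious TEAE table for PS0010 and PS0011 combined, with the clock starting at the first PS0010 dose, and four TEAE tables by PS0010 Week 12 PASI90 status.

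**The concern.** A reader of the primary table will compare its dose columns, but those columns differ in more than dose. The 160mg column mixes subjects taking bimekizumab for the first time with subjects already 12 weeks on it. The other two bimekizumab columns contain no first-time users.

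Selection adds to this. Protocol 6.1 requires every entrant to have completed PS0010 dosing without meeting a withdrawal criterion. The 64mg and 320mg subjects met that condition while on bimekizumab, and the placebo-to-160mg subjects met it while on placebo.

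If some events cluster soon after first exposure, they are counted at 160mg. For the other doses they fell in PS0010 and are outside the primary table. A 160mg difference could then be taken for a dose effect, or a real dose trend could be blurred, in the study's primary safety result.

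**Working it through.** **Time at risk, checked first.** SAP 7 expects 24 injections, two per dose, so 12 doses at Weeks 0 to 44. Adding the 20-week follow-up gives 44 + 20 = 64 weeks, the maximum duration in Protocol 5.1.1. Also 20 × 7 = 140 days, as in Protocol 14.3.1. A completer therefore contributes 64 weeks at risk, of which a naive subject spends 12 in the first 12 weeks on drug.

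**Assumptions, none given in the documents.**
- 40 per PS0010 arm: 240 / 6 regimens. Protocol 2.2.1 prints a five-term ratio but lists six regimens.
- Full rollover and 64 weeks at risk for everyone.
- Almost no placebo PASI90 response (1 of 40), so 39 naive subjects.
- PASI90 response of 30-60% on 64mg, giving 28 to 16 non-responders moving to 160mg.
- PASI90 response of 50-80% in the two 160mg arms together (80 subjects), giving 40 to 64 responders staying on 160mg.
- k, the ratio of the AE rate in the first 12 weeks on drug to the later rate, at 1, 1.5 and 2.

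**Naive share of the 160mg column**, s = 39 / (39 + 64mg non-responders + 160mg responders), and **EAER inflation** = s × (12/64) × (k − 1):

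| PASI90 on 64mg / 160mg | s | k = 1 | k = 1.5 | k = 2 |
|---|---|---|---|---|
| 30% / 80% | 39/131 = 30% | 0% | 2.8% | 5.6% |
| 60% / 80% | 39/119 = 33% | 0% | 3.1% | 6.1% |
| 30% / 50% | 39/107 = 36% | 0% | 3.4% | 6.8% |
| 60% / 50% | 39/95 = 41% | 0% | 3.8% | 7.7% |

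In the 64mg and 320mg columns s = 0, so the first-exposure term is 0% in every row.

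**EAIR.** This measure carries the confidence interval and stops each affected subject's clock at the first event. I used a constant hazard of kλ for 12 weeks, then λ for 52 weeks, with λ = 0.1, 0.5 and 2 per year. Over the same four rows the 160mg EAIR rises by about 3-8% at k = 1.5 and 6-15% at k = 2, more for common events.

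**Do the combined tables cure it?** SAP 8.2.1 does not specify their columns. If they follow the dose being taken, the share of person-time that falls in the first 12 weeks on drug is:
- 64mg: 40 × 12 = 480 early weeks. The total is 480 + 64 × 12 = 1248, or 480 + 64 × 24 = 2016. Share 38% or 24%.
- 160mg: (80 + 39) × 12 = 1428 early weeks. The total is 960 + 64 × (95 to 131) = 7040 to 9344. Share 20% to 15%.
- 320mg: 480 early weeks. The total is 480 + 64 × (96 to 120) = 6624 to 8160. Share 7% to 6%.
- 480mg: 100%, because all these subjects move to 320mg.

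In the primary table the corresponding shares are s × 12/64, about 6-8% for 160mg, and 0% for 64mg and 320mg. The combined tables count everyone's first 12 weeks, but they remain unbalanced on time since first dose, in a different pattern.

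**The case against.** The strongest reply is that the SAP already looks beyond the primary table. The combined tables start the clock at the first PS0010 dose and contain attribution rules for the switch date, so early events at every dose are reported somewhere. The responder-status tables include fungal infections. If they are also laid out by dose, the 160mg responder cell would contain no naive subjects. This stands in part. However, the columns of the combined tables are not specified and their early-exposure shares are uneven. The responder-status tables are not specified to isolate naive subjects either: the non-responders entering 160mg come from both placebo and 64mg.

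A second reply is that the study is descriptive, its objective is long-term safety, and the shift is small against sampling error. That is fair. With 20 affected subjects, the exact Poisson 95% interval runs from 39% below the rate to 54% above it.

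Three stronger readings do not hold:

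- A reader might infer that the 160mg rates *are* inflated. The documents give no early or late AE rate, and at k = 1 nothing changes.
- A reader might infer that events around a treatment change affect one column only. Former 160mg non-responders step up within the 320mg column, so events linked to a dose increase can appear there.
- A reader might see the sponsor conceding the point for laboratory data, because Protocol 14.3.2 says that "the initial values can be impacted by the randomized treatment in PS0010". That reasoning concerns values followed over visits. SAP 8.2.2, 8.2.3 and 8.2.5 also present laboratory, vital-sign and ECG changes by PS0011 group, so there is no such contrast with AEs in the SAP.

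**Conclusion.** The confounding follows from the assignment rules and needs no assumption: barring dosing errors, all first-time bimekizumab users are in the 160mg column and none are in the 64mg or 320mg columns. SAP 8.1.1 assigns events by dose at onset, which gives the same columns unless there is a dosing error.

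The numerical effect is conditional. Under the stated assumptions on arm size, rollover and response, naive subjects make up about 30-41% of the 160mg column. The column's EAER is raised by 0% at equal rates, about 3-4% at 1.5 times and about 6-8% at twice the later rate. Subjects withdrawn early have less time at risk, which would give early events more weight than shown.

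This does not invalidate the primary analysis. It limits what the dose columns can support, and it can be remedied cheaply.

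**What to change.** In SAP 8.1.6 and 8.2.1, also present the overall, serious and fungal-infection EAIR and EAER by the PS0010/PS0011 treatment groups defined in SAP 3.6. At the least, split the 160mg column into placebo to 160mg and previously treated. State in the SAP that a difference at 160mg will not be read as a dose effect without that split. Specify the columns of the combined PS0010 and PS0011 tables.

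The cost is SAP wording and a re-run of existing tables with another grouping variable. The downside is smaller columns: in the scenarios above the 64mg group has only 12 to 24 subjects, and taking out 39 naive subjects leaves 56 to 92 previously treated subjects at 160mg. The previously treated columns would still differ in PS0010 response and in dose change on entry, so statements about dose stay descriptive.
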